#### **10.1.8.2 Monitoring**

- The investigator must permit trial-related monitoring, audits, IRB/IEC review, and regulatory agency inspections and provide direct access to source data documents (original documents, data and records). Direct access includes permission to examine, analyse, verify and reproduce any record(s) and report(s) that are important to the evaluation of the trial. If the electronic medical record does not have a visible audit trail, the investigator must provide the monitor with signed and dated printouts. In addition, the relevant site staff should be available for discussions at monitoring visits and between monitoring visits (e.g. by telephone).
- Trial monitors will perform ongoing source data verification to confirm that data entered into the eCRF by authorised site personnel are accurate, complete and verifiable from source documents; that the safety and rights of patients are being protected, to monitor drug accountability and collect completed paper CRF pages, if applicable, and that the trial is being conducted in accordance with the currently approved protocol and any other trial agreements, ICH GCP, and all applicable regulatory requirements.
- Monitoring will be conducted using a risk-based approach including risk assessment, monitoring plans, centralised monitoring (remote assessment of data by Novo Nordisk) and visits to sites.
- Monitors will review the patient's medical records and other source data, e.g. the diaries, to ensure consistency and/or identify omissions compared to the eCRF.

#### **10.1.8.3 Protocol compliance**

Deviations from the protocol should be avoided. If deviations do occur, the investigator must inform the monitor without delay and the implications of the deviation must be reviewed and discussed.

Deviations must be documented and explained in a protocol deviation by stating the reason, date, and the action(s) taken. Some deviations, for which corrections are not possible, can be acknowledged and confirmed via edit checks in the eCRF or via listings from the trial database.

#### **10.1.9 Source documents**

All data entered in the eCRF must be verifiable in source documentation other than the eCRF.

If source data is entered directly in a paper CRF, each data entry or clear series of data entries must be signed and dated separately by the site staff making the entry.

- The original of the completed diaries must not be removed from the site, unless they form part of the CRF and a copy is kept at the site.
- Source documents provide evidence for the existence of the patient and substantiate the integrity of the data collected. Source documents are filed at the site.
- Data reported on a paper CRF or entered in the eCRF that are transcribed from source documents must be consistent with the source documents, or the discrepancies must be explained. The investigator may need to request previous medical records or transfer records. Also, current medical records must be available.
- It must be possible to verify patient's medical history in source documents, such as patient's medical record.
- The investigator must document any attempt to obtain external medical information by noting the date(s) when information was requested, and who was contacted.
- Definition of what constitutes source data can be found in a source document agreement at each site. There will only be one source document defined at any time for any data element.

#### **10.1.10 Retention of clinical trial documentation**

- Records and documents, including signed informed consent forms, pertaining to the conduct of this trial must be retained by the investigator for 15 years after end of trial unless local regulations or institutional policies require a longer retention period. No records may be destroyed during the retention period without the written approval of Novo Nordisk. No records may be transferred to another location or party without written notification to Novo Nordisk.
- The investigator must be able to access his/her trial documents without involving Novo Nordisk in any way. If applicable, eCRF and other subject data will be provided in an electronic readable format to the investigator before access is revoked to the systems supplied by Novo Nordisk. Site-specific CRFs and other patient data (in an electronic readable format or as paper copies or prints) must be retained by the site. A copy of all data will be stored by Novo Nordisk.
- Patient's medical records must be kept for the maximum period permitted by the hospital, institution or private practice.
- Site specific data should only be stored at site.
- Long-term storage of Chinese patient's trial data is not allowed in other entities.

#### **10.1.11 Trial and site closure**

Novo Nordisk reserves the right to close the site or terminate the trial at any time for any reason at the sole discretion of Novo Nordisk. If the trial is suspended or terminated, the investigator must inform the patients and/or the patient's LAR promptly and ensure appropriate therapy and follow-up. The investigator and/or Novo Nordisk must also promptly inform the regulatory authorities and IRBs/IECs and provide a detailed written explanation.

Sites will be closed upon trial completion. A site is considered closed when all required documents and trial supplies have been collected and a site closure visit has been performed.

The investigator may initiate site closure at any time, provided there is reasonable cause and sufficient notice is given in advance of the intended termination.

Reasons for the early closure of a site by Novo Nordisk or investigator may include but are not limited to:

- failure of the investigator to comply with the protocol, the requirements of the IRB/IEC or local health authorities, Novo Nordisk procedures or GCP guidelines.
- inadequate recruitment of patients by the investigator.
- discontinuation of further trial product development.

### **10.1.12 Responsibilities**

The investigator is accountable for the conduct of the trial at his/her site and must ensure adequate supervision of the conduct of the trial at the site. If any tasks are delegated, the investigator must maintain a log of appropriately qualified persons to whom he/she has delegated specified trial-related duties. The investigator must ensure that there is adequate and documented training for all staff participating in the conduct of the trial. It is the investigator's responsibility to supervise the conduct of the trial and to protect the rights, safety, and well-being of the patients.

A qualified physician, who is an investigator or a sub-investigator for the trial, must be responsible for all trial-related medical decisions.

The investigator is responsible for filing essential documents (i.e. those documents which individually and collectively permit evaluation of the conduct of a trial and the quality of the data produced) in the investigator trial master file. The documents, including the patient identification code list must be kept in a secure locked facility so that no unauthorized persons can get access to the data.

The investigator will take all necessary technical and organisational safety measures to prevent accidental or wrongful destruction, loss or deterioration of data. The investigator will prevent any unauthorised access to data or any other processing of data against applicable law. This also includes ensuring that no indirect sharing of user credentials for IT systems used in this study takes place (e.g. by not sharing IT equipment with others in a way where user credentials have the possibility of being shared). The investigator must be able to provide the necessary information or otherwise demonstrate to Novo Nordisk that such technical and organisational safety measures have been taken.

During any period of unavailability, the investigator must delegate responsibility for medical care of patients to a specific qualified physician who will be readily available to patients during that time.

If the investigator is no longer able to fulfil the role as investigator (e.g. if he/she moves or retires), a new investigator will be appointed in consultation with Novo Nordisk.

The investigator and other site personnel must have sufficient English skills according to their assigned task(s).

### **10.1.13 Indemnity statement**

Novo Nordisk carries product liability for its products, and liability as assumed under the special laws, acts and/or guidelines for conducting clinical trials in any country, unless others have shown negligence.

Novo Nordisk assumes no liability in the event of negligence or any other liability of the sites or investigators conducting the trial or by persons for whom the said site or investigator are responsible.

Novo Nordisk accepts liability in accordance with Chinese law and regulations.

### **10.1.14 Publication policy**

The information obtained during the conduct of this trial is considered confidential and may be used by or on behalf of Novo Nordisk for regulatory purposes as well as for the general development of the trial product. All information supplied by Novo Nordisk in connection with this trial shall remain the sole property of Novo Nordisk and is to be considered confidential information.

No confidential information shall be disclosed to others without prior written consent from Novo Nordisk. Such information shall not be used except in the performance of this trial.

The information obtained during this trial may be made available to other investigators who are conducting other clinical trials with the trial product, if deemed necessary by Novo Nordisk. Provided that certain conditions are fulfilled, Novo Nordisk may grant access to information obtained during this trial to researchers who require access for research projects studying the same disease and/or trial product studied in this trial.

Novo Nordisk may publish on its clinical trials website a redacted CTR for this trial.

One investigator will be appointed by Novo Nordisk to review and sign the CTR (signatory investigator) on behalf of all participating investigators.

#### **10.1.14.1 Communication of results**

Novo Nordisk commits to communicate and disclose results of trials regardless of outcome. Disclosure includes publication of a manuscript in a peer-reviewed scientific journal, abstract submission with a poster or oral presentation at a scientific meeting or disclosure by other means.

The results of this trial will be subject to public disclosure on external web sites according to international and national regulations. Novo Nordisk reserves the right to defer the release of data until specified milestones are reached, for example when the CTR is available. This includes the right not to release the results of interim analyses, because the release of such information may influence the results of the entire trial.

At the end of the trial, one or more scientific publications may be prepared collaboratively by the investigator(s) and Novo Nordisk. Novo Nordisk reserves the right to postpone publication and/or communication for up to 60 days to protect intellectual property.

In all cases, the trial results will be reported in an objective, accurate, balanced and complete manner, with a discussion of the strengths and limitations. In the event of any disagreement on the content of any publication, both the investigators' and Novo Nordisk opinions will be fairly and sufficiently represented in the publication.

#### **10.1.14.2 Authorship**

Novo Nordisk will work with one or more investigator(s) and other experts who have contributed to the trial concept or design, acquisition, analysis or interpretation of data to report the results in one or more publications.

Authorship of publications should be in accordance with the Recommendations for the Conduct, Reporting, Editing and Publication of Scholarly Work in Medical Journals by the International Committee of Medical Journal Editors.

All authors will be provided with the relevant statistical tables, figures, and reports needed to evaluate the planned publication.

Where required by the journal, the investigator from each site will be named in an acknowledgement or in the supplementary material, as specified by the journal.

#### **10.1.14.3 Site-specific publication(s) by investigator(s)**

For a multicentre clinical trial, analyses based on single-site data usually have significant statistical limitations and frequently do not provide meaningful information for healthcare professionals or patients, and therefore may not be supported by Novo Nordisk. Thus, Novo Nordisk may deny a request or ask for deferment of the publication of individual site results until the primary manuscript is accepted for publication. In line with Good Publication Practice, such individual reports should not precede the primary manuscript and should always reference the primary manuscript of the trial.

#### **10.1.14.4 Investigator access to data and review of results**

As owner of the trial database, Novo Nordisk has the discretion to determine who will have access to the database. Individual investigators will have their own research patients' data.

## 10.2 Appendix 2: Clinical laboratory tests

- The tests detailed in [Table 10-1](#) and [Table 10-2](#) will be performed by the central laboratory unless otherwise stated (except for urinalysis; see below).
- Urinalysis will be performed locally with sticks provided by the central laboratory. Results of urinalysis should be recorded in the eCRF. Results from the urinalysis other than those listed in [Table 10-2](#) should not be reported to Novo Nordisk. Clinically significant findings must be recorded as concomitant illness at screening and as AEs at the following visits if it is a new finding or a change relative to a previous visit.
- At visits where it is not possible to perform the required blood sampling, re-scheduling of the visit within the visit window (see Section [1.2](#)) should be done. The timing of sampling in relation to trial drug administration should always be followed.
- Additional tests may be performed at any time during the trial as determined necessary by the investigator or required by local regulations. Only laboratory samples specified in the protocol should be sent to the central laboratory for analysis; if additional laboratory sampling is needed, e.g. to follow up on AEs, this must be done at a local laboratory.
- The central laboratory will communicate to the investigator abnormal values of parameters not requested in the protocol but identified by the laboratory equipment and/or their processes according to their laboratory SOPs. These data will not be transferred to the trial database. The investigator should review such values for AEs and report these according to this protocol.
- The investigator must review all laboratory results for concomitant illnesses and AEs.
- Laboratory samples will be destroyed no later than at finalisation of the CTR.
- The inhibitor samples will be stored at a central laboratory after end of trial and until marketing authorisation approval or until the research project terminates, after which they will be destroyed.

### Blood sampling volume

The investigator should follow local guidelines such as the European guideline for blood sampling and volume of blood at each visit in relation to the patient's body weight and age.

**Table 10-1 Protocol-required efficacy laboratory assessments**

Laboratory assessments	Parameters
FIX activity	FIX activity

**Table 10-2 Protocol-required safety laboratory assessments**

Laboratory assessments	Parameters
Antibody assessments	

• Anti-N9-GP antibodies (including indirect detection of anti-PEG antibodies)

• FIX inhibitors

• Anti-HCP antibodies

Haematology	

• Erythrocytes

• Haemoglobin

• Leukocytes

• Thrombocytes

• Differential count (lymphocytes, monocytes, neutrophils, eosinophils, basophils)

Biochemistry	

Alanine Aminotransferase (ALT)

Albumin

Alkaline phosphatase

Aspartate Aminotransferase (AST)

Creatinine

Bilirubin, total

C-reactive protein (CRP)

Urea

Virology	

Hepatitis B surface antigen (HBsAg)

Hepatitis C virus antibody

HIV 1+2 screen (if positive test, then a confirmatory test is performed. If the confirmatory test is also positive, then assessment of viral load is performed)

CD4+ T cell count (only at screening)

Coagulation parameters	

Activated partial thromboplastin time (aPTT)

International normalised ratio (INR)

Prothrombin time (PT)

Lupus anticoagulant

Urinalysis	

pH

Protein

Erythrocytes

Leukocytes

Glucose

Albumin/creatinine ratio

Other tests	

eGFR calculated by the central laboratory based on the creatinine value using the MDRD equation

PEG plasma concentration

Notes:	Details of required actions for increased liver parameters are given in Section 10.3 (Hy's Law).

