Factor IX activity f	8.1.2 8.5		X	X	X	X	X	X	X	X	X		X		X
Anti-N9-GP antibodies/Anti-PEG antibodies	8.6.1	X	X	X	X	X	X	X	X	X	X		X		
FIX inhibitor analysis	8.6.2	X	X	X	X	X	X	X	X	X	X		X		X

Procedure	Protocol section	Screening	Baseline	Treatment period								End of treatment	Discontinuation of treatment	Surgery j
				V1	V2	V3	V4	V5	V6	V7 a	V8 b			
Visit														
Timing of visit		-2 weeks	0	4 weeks	8 weeks	12 weeks	20 weeks	28 weeks	36 weeks	44 weeks	50 weeks			30 days
Visit window		-7 days		±7 days	±7 days	±7 days	±7 days	±7 days	±7 days	±7 days	±7 days	+56 days c		+5 days
End of treatment	6.7 7.1											X	X	
End of trial	4.4													X
Hand out ID card		X												
Hand out and instruct in diary	8.7		X	X	X	X	X	X	X	X	X			
Training in trial product			X											

a In Arm A (On-demand/PPX), patients will switch from on-demand treatment to PPX treatment at Visit 7.

b In Arm A (On-demand/PPX), Visits 8 and 9 will only be conducted in case the patient has not yet attained 30 EDs in the trial (including treatment of bleeds during the on-demand period as well as scheduled once-weekly PPX doses and treatment of breakthrough bleeds during the PPX period) (see Section [4.1](#) for details).

c The visit window of +56 days for Visit 10 is included to ensure that patients who have not achieved the required number of exposure days after 50 weeks of treatment can have the treatment period extended until maximum 58 weeks as needed (see Section [4.1](#) for details).

d Only in patients <18 years.

e Only bleeding episodes after first dose of trial product in Arm B.

f All patients will have FIX activity measurements pre-dosing and 30 minutes post-dosing at all dosing visits during PPX treatment and during surgery.

g For details on pharmacokinetic assessments, refer to [Table 1-1](#).

h Only applicable in Arm B.

i Only to be assessed in case of an acute severe allergic/anaphylactic reaction.

j Please also see surgery specific flowchart in [Table 1-2](#).

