### 5.1 Inclusion criteria

Patients are eligible to be included in the trial only if all of the following criteria apply:

1. Informed consent obtained before any trial-related activities. Trial-related activities are any procedures that are carried out as part of the trial, including activities to determine suitability for the trial.
2. Male Chinese patient with moderate to severe congenital haemophilia B with a FIX activity  $\leq 2\%$  according to medical records.
3. Aged 12-70 years (both inclusive) at the time of signing informed consent.
4. History of at least 100 EDs to products containing FIX.
5. Patients currently on prophylaxis or patients currently treated on-demand with at least 6 bleeding episodes during the last 12 months or at least 3 bleeding episodes during the last 6 months.
6. The patient, legally authorised representative (LAR) and/or caregiver are capable of assessing a bleeding episode, keeping a diary, performing home treatment of bleeding episodes and otherwise following the trial procedures.

 Prophylaxis, prevention, on-demand and treatment during surgery counts as exposure days. If not possible to count the actual number of exposures in the medical chart, the investigator should make a written statement with an estimate based on e.g. patient age, treatment frequency, medical history, discussion with previous doctor/transfer note and other relevant information. This statement should be filed either with the patient chart or separately with the investigator trial file.

The criteria will be assessed at the investigator's discretion unless otherwise stated.

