### 5.2 Exclusion criteria

Patients are excluded from the trial if any of the following criteria apply:

1. Known or suspected hypersensitivity to trial product or related products.
2. Previous participation in this trial. Participation is defined as signed informed consent.
3. Participation in any clinical trial of an approved or non-approved investigational medicinal product within 5 half-lives or 30 days from screening, whichever is longer.
4. Known history of FIX inhibitors based on existing medical records, laboratory report reviews and patient and LAR interviews.
5. Current FIX inhibitors  $\geq 0.6$  BU.
6. HIV positive, defined by medical records, with CD4+ count  $\leq 200/\mu\text{L}$  and a viral load  $>200$  particles/ $\mu\text{L}$  or  $>400000$  copies/mL within 6 months of the trial entry. If the data are not available in the medical records within the last 6 months, then the test must be performed at the screening visit.
7. Congenital or acquired coagulation disorder other than haemophilia B.
8. Previous arterial thrombotic events (e.g. myocardial infarction and intracranial thrombosis) or previous deep venous thrombosis or pulmonary embolism (as defined by available medical records).

9. Hepatic dysfunction defined as aspartate aminotransferase (AST) and/or alanine aminotransferase (ALT)  $>3$  times the upper limit of normal combined with total bilirubin  $>1.5$  times the upper limit of normal at screening.
10. Renal impairment defined as estimated glomerular filtration rate (eGFR)  $\leq 30$  mL/min/1.73 m^2 for serum creatinine measured at screening.
11. Any disorder, except for conditions associated with haemophilia B, which in the investigator's opinion might jeopardise the patient's safety or compliance with the protocol.
12. Platelet count  $<50 \times 10^9$ /L at screening.
13. Immune modulating or chemotherapeutic medication.
14. Mental incapacity, unwillingness or language barriers precluding adequate understanding or cooperation.

The criteria will be assessed at the investigator's discretion unless otherwise stated.

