### 9.2 Sample size determination

No formal sample size calculations have been performed. Based on meeting communication with CDE, a total number of 24 Chinese patients to complete this trial is assessed to be sufficient to evaluate efficacy and safety in the Chinese population, considering that data are also available from the global pivotal trial NN7999-3747, which included Asian patients. In order to account for withdrawn patients, 30 patients will be started on trial product (15 patients in Arm A [on-demand/PPX] and 15 patients in Arm B [PPX]).

All 15 patients in Arm B will participate in the pharmacokinetic evaluation to ensure that at least 12 patients will complete single-dose and steady-state pharmacokinetic profiles.

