### **10.3.3 Description of AESIs and AEs requiring additional data collection**

#### **Description of AESIs and AEs requiring additional data collection (on specific event form)**

##### **AESIs**

An AESI is an event which, in the evaluation of safety, has a special focus due to requirements from regulatory authorities.

A serious AESI should be reported following the same reporting requirements and timelines as for SAEs (see Section [10.3.5](#)).

The following are defined as AESIs in this trial:

- **Inhibitor formation against FIX** is always considered a serious AESI. If an investigator obtains any indication of inhibitor formation by clinical signs or central laboratory results, this should be reported as a serious AESI. Please update the reported serious AESI with inhibitor tests results, when these are available.

- **Allergic reaction** including, but not limited to, any acute IgE mediated reaction or delayed type hypersensitivity (clinical signs may include various types of skin rashes) that does not meet the definition of anaphylaxis as described by Sampson et al. (see below).
- **Anaphylactic reaction** as defined by Sampson et al. (see below).
- **CNS-related AEs** including, but not limited to, any learning and behavioural deficits. Examples include but are not limited to:
  - Headache
  - Seizures
  - Vision problems
  - Acute changes in mental status
  - Developmental, cognitive or behavioural issues.
- **Thromboembolic events** (clinical signs or laboratory indications of arterial and venous thrombosis including myocardial infarction, pulmonary embolism, cerebral infarction/thrombosis, deep vein thrombosis, other clinically significant thromboembolic events and peripheral artery occlusion, see definitions below).
- **Renal AEs** including new onset of renal disorder or renal impairment or acute and chronic renal failure.

AESIs must always be reported on an AE form and safety information form in the eCRF.

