5.6 Other safety analyses

All additional safety parameters such as laboratory parameters, vital signs and physical examinations will be summarised and listed.

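### MDRD is the only eGFR equation for patients from age 12, so the renal exclusion criterion probably works at a different level in adolescents (minor)

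*Protocol*

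**What the plan says.** - **Equation.** Protocol Appendix 2, Table 10-2, lists under other tests: "eGFR calculated by the central laboratory based on the creatinine value using the MDRD equation". No other eGFR equation and no age restriction appear in the protocol or the SAP.
- **Age.** Protocol Section 5.1, criterion 3: "Aged 12-70 years (both inclusive) at the time of signing informed consent". Minors from 12 are therefore eligible.
- **Use for eligibility.** Protocol Section 5.2, criterion 10, excludes patients with an eGFR of 30 mL/min/1.73 m² or below, from creatinine measured at screening. The limit is the same at every age. Section 5 rules out waivers of eligibility criteria.
- **Height.** The flowchart in Protocol Section 1.2 has height measured at screening in all patients. Two later measurements carry the footnote "Only in patients <18 years".
- **Other renal information.** Table 10-2 also requires creatinine, urea, urine protein and "Albumin/creatinine ratio". Renal AEs are events of special interest, described in Section 10.3.3 as "including new onset of renal disorder or renal impairment or acute and chronic renal failure", with no eGFR cut-off.
- **Analysis.** SAP Section 5.6: "All additional safety parameters such as laboratory parameters, vital signs and physical examinations will be summarised and listed". Protocol Section 9.4.4 says the same and adds neurological examinations.

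**The concern.** Creatinine depends on muscle mass as well as on kidney function, and muscle mass changes through adolescence. Paediatric equations deal with this through height. MDRD uses no height, so the same MDRD value need not mean the same renal function in a growing boy and in a man. The protocol recognises growth in patients under 18, since it re-measures their height, but it does not carry this into the eGFR calculation and gives no reason for using MDRD at these ages.

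What is at stake is whether criterion 10 means the same thing across the eligible age range. If MDRD reads high in adolescents, a boy at the intended limit would pass screening.

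**Working it through.** The documents give no eGFR value, formula, creatinine unit or creatinine assay, so there is no figure of theirs to reproduce. The check below is an illustration under stated assumptions.

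**Inputs from the documents:** MDRD for all (Table 10-2); eligible from age 12 (Section 5.1); limit of 30 mL/min/1.73 m² (Section 5.2).

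**Assumed inputs:**
- MDRD, male, standardised creatinine, no ethnic factor: 175 × Scr^−1.154 × age^−0.203, with Scr in mg/dL.
- Height-based paediatric equation: k × height (cm) / Scr, with k = 0.413 (current bedside Schwartz, standardised creatinine). As a range check, k = 0.7 (older constant for adolescent boys).
- Ages 12 to 17, heights 140 to 185 cm, Scr 0.5 to 3.0 mg/dL.

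**Step 1, level, k = 0.413.**
- Age 12, 150 cm, Scr 0.7: MDRD 159; height-based 0.413 × 150 / 0.7 = 88; ratio 1.80.
- Age 17, 175 cm, Scr 0.9: MDRD 111; height-based 0.413 × 175 / 0.9 = 80; ratio 1.38.
- Over the whole grid MDRD is higher in every case. The ratio runs from 1.09 (age 17, 185 cm, Scr 3.0) to 2.03 (age 12, 140 cm, Scr 0.5).

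**Step 2, the exclusion limit, k = 0.413.** The height-based value is 30 at Scr = 0.413 × height / 30. MDRD is 30 at Scr = (175 × age^−0.203 / 30)^(1/1.154).

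| Age, height | Scr at height-based 30 | Scr at MDRD 30 | MDRD when height-based = 30 |
|---|---|---|---|
| 12, 140 cm | 1.93 | 2.98 | 49.6 |
| 12, 150 cm | 2.06 | 2.98 | 45.8 |
| 15, 168 cm | 2.31 | 2.86 | 38.4 |
| 17, 175 cm | 2.41 | 2.80 | 35.7 |
| 17, 185 cm | 2.55 | 2.80 | 33.5 |

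A boy is classified differently only if his creatinine lies between the second and third columns, that is, somewhere within about 1.9 to 3.0 mg/dL. The band narrows as age and height increase.

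**Step 3, range check, k = 0.7.** The ratio of MDRD to the height-based value now runs from 0.64 to 1.20. At the limit the order reverses: the height-based value reaches 30 at Scr 3.27 to 4.32, above the MDRD figures of 2.80 to 2.98, so MDRD would be the stricter of the two. Pairing coefficient 175 with k = 0.7 mixes calibrations, so Steps 1 and 2 are the more coherent comparison. Step 3 does show that the direction depends on the assay and on the constant that goes with it.

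**Step 4, change within a patient.** For a boy of 12 and 150 cm whose creatinine doubles from 0.6 to 1.2, MDRD goes from 191 to 86, a fall of 55% (1 − 2^−1.154). The height-based value goes from 103 to 52, a fall of 50%. MDRD moves by slightly more, not less.

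**The case against.** The strongest case against the point is that it leans on equations found nowhere in the documents and that little turns on it. Most of this stands.

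- **Assumed equations.** Neither document gives a formula or an assay, and neither says that MDRD is meant for adults only. Overstatement in adolescents is therefore likely under a stated assumption and cannot be asserted as fact (Step 3).
- **Eligibility.** A boy in the affected band has a markedly raised creatinine, which is reported in its own right. Criterion 11 also lets the investigator exclude any disorder thought to jeopardise safety. The number of adolescents among the 30 patients is not given.
- **Monitoring.** A reader might infer that a large loss of renal function in an adolescent could pass unnoticed during treatment. The documents do not support that. Proportional change is preserved (Step 4), Section 8.2.5 has laboratory abnormalities judged against baseline or earlier results, and creatinine, urea, urinalysis and clinically defined renal events do not depend on MDRD. The copy of the flowchart available to me does not show at which visits eGFR is reported, so nothing here rests on that.
- **PEG.** A reader might also link the point to the potential risk of PEG accumulation in Section 2.4.1. That section makes no connection with eGFR, and PEG plasma concentration is a separate test in Table 10-2.

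What the objection does not remove is the gap itself: an age-blind limit is applied to minors through an equation with no height term, without justification, although height is already measured.

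**Conclusion.** The point holds as a minor one. Table 10-2 names MDRD for all patients, and criterion 10 applies the result to boys from 12 with no age rule. Assuming standardised creatinine, coefficient 175 and k = 0.413, MDRD likely overstates adolescent eGFR by a ratio of about 1.1 to 2.0, and a height-based 30 reads as about 33 to 50. With older calibrations the direction is open.

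The consequence is confined to the level of eGFR in patients under 18 and, at screening, to the rare adolescent with creatinine of roughly 1.9 to 3.0 mg/dL. No endpoint, model, sample size or error rate is affected, because laboratory data are only summarised and listed. The wider reading, that renal safety monitoring or the PEG risk assessment is compromised, is not supported.

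**What to change.** In Table 10-2 and the laboratory manual:

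- For patients under 18 at screening, have the central laboratory calculate eGFR with a height-based paediatric equation matched to its creatinine assay (bedside Schwartz if creatinine is standardised), using the most recent measured height.
- For adults, keep MDRD.
- Leave the threshold in criterion 10 as it is.
- Keep each patient on the equation assigned at screening throughout the trial, so that a boy who turns 18 does not show an artificial step.

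If the sponsor prefers MDRD for all ages, the protocol should say why it is suitable for patients under 18 with the assay in use.

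The cost is one line in each of the two documents. Height is already collected, so no procedure is added. The downside is two equations in the eGFR listing, which should show which one was used for each patient.
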